5.3 TREATMENT ARMS

5.3.1 Treatment Arm 1: Experimental

Rivaroxaban 2.5 mg twice daily for 90 days (rivaroxaban will be started 6 to 8 hours after the finalization of the procedure³⁷) and 325mg of ASA on Day 1, plus 81 mg of ASA daily for 89 days. After 90 days, the study treatment will be discontinued and subsequent treatment will be at the discretion of the attending physician.

5.3.2 Treatment Arm 2: Standard of care

Clopidogrel 300mg on Day 1 (loading dose), then 75 mg daily for 89 days and 325mg of ASA on Day 1 then 81 mg of ASA daily for 89 days. After 90 days, the study treatment will be discontinued and subsequent treatment will be at the discretion of the attending physician

5.4 PROHIBITED MEDICATIONS DURING THE STUDY:

Systemic treatment with strong CYP 3A4 and P-glycoprotein inhibitors (such as ketoconazole, itraconazole, posaconazole, or ritonavir) is a contra-indication to treatment with Rivaroxaban and is therefore an exclusion criteria for study entry.

If a participant in the rivaroxaban arm requires initiation of treatment with strong CYP 3A4 and P-glycoprotein inhibitor while on study treatment the participant will be withdrawn from study treatment. The participant may then be switched to an alternative anticoagulant treatment at the discretion of the attending physician. See appendix 3 for a list of CYP 3A4 and P glycoprotein inhibitors.

5.5 FORMULATION PACKAGING AND LABELING

ASA and clopidogrel will be purchased and relabeled for this trial according to the template below. Rivaroxaban will be provided by Bayer and will be labeled according to the template below. All three study medications will be provided to the participants in bulk format. Each participant will be given a 90 day supply of study drug (according to the randomization scheme) at Day 1.

Product information for each of the study medications is listed in Appendix 4.

Rivaroxaban 2.5 mg Expiration: DD-MMM-YYYY Store at room temperature between +15°C and +25°C Lot # ----- Protocol name : RIFLE Trial Sponsor: The Ottawa Hospital Research Institute, [name] Investigational drug -- to be used only by a qualified Investigator	Rivaroxaban 2.5 mg Expiration: DD-MM-YYYY Conserver au l'air ambiant , entre +15°C et +25°C, Lot # ----- Nom du Protocole: RIFLE Trial Commanditaire: Institut de recherche de l'Hôpital d'Ottawa [name] Médicament expérimental -- à être utilisé seulement par un Investigateur qualifié
Clopidogrel 75 mg Expiration: DD-MMM-YYYY Store at room temperature between +15°C and +25°C Lot # ----- Protocol name : RIFLE Trial Sponsor: The Ottawa Hospital Research Institute, [name] Investigational drug -- to be used only by a qualified Investigator	Clopidogrel 75 mg Expiration: DD-MM-YYYY Conserver au l'air ambiant , entre +15°C et +25°C, Lot # ----- Nom du Protocole: RIFLE Trial Commanditaire: Institut de recherche de l'Hôpital d'Ottawa [name] Médicament expérimental -- à être utilisé seulement par un Investigateur qualifié
ASA 81 mg Expiration: DD-MMM-YYYY Store at room temperature between +15°C and +25°C Lot # ----- Protocol name : RIFLE Trial Sponsor: The Ottawa Hospital Research Institute, [name] Investigational drug -- to be used only by a qualified Investigator	ASA 81 mg Expiration: DD-MM-YYYY Conserver au l'air ambiant , entre +15°C et +25°C, Lot # ----- Nom du Protocole: RIFLE Trial Commanditaire: Institut de recherche de l'Hôpital d'Ottawa [name] Médicament expérimental -- à être utilisé seulement par un Investigateur qualifié

5.6 ACCOUNTABILITY AND STORAGE

Study drug will be stored and maintained by the Clinical Trial pharmacy technicians at The Ottawa Hospital. Bulk accountability logs and individual accountability logs will be completed and maintained by the pharmacy technicians. Participants will keep a diary card. Drug accountability (pill count & review of diary cards) will be done on Day 90 when the medication is returned.

Participants will be counseled to keep the study drug in room temperature conditions. The study medication which they take home should not be exposed to extreme temperatures.

5.7 INDIVIDUAL PARTICIPANT COMPLIANCE

When discharged from hospital participants will be given a diary and will record the date and time of administration of each dose. If a dose is missed the participant should take it as soon as it is remembered and record the time. The next dose should be taken at the new time. Non-adherent participants may be removed from the study at the discretion of the primary investigator. In order to allow drug accountability by research staff participants will be instructed to return all bottles of study medication.

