5.8 CONCOMITANT MEDICATIONS

Medication that the participant is taking from the screening time point until study end at 12 months will be recorded by the Research Coordinator. This includes any herbal supplements and vitamins and over the counter medications.

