6 STUDY PROCEDURES AND EVALUATIONS

6.1 STUDY VISITS

All participants will be followed for 12 months following their angioplasty. Participants will return to The Ottawa Hospital or will be evaluated as an inpatient at 7 days. There are follow up visits at 30 days, 90 days, 6 months, and 12 months post randomization. All primary and secondary outcome data will be collected during the trial (7 days, 30 days, 90 days, 6 months and 12 months) so that procedures can be evaluated and optimized for future studies. The schedule of study events is summarized in a table in appendix 1.

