6.3.3 Duplex ultrasound arterial examination

Duplex ultrasound arterial examination will be performed at the Ottawa Civic Hospital (Diagnostic Imaging) at 30 days, 6 and 12 months as part of the routine care. The following will be recorded in the CRF : re-stenosis as defined by peak velocity flow, and the Ankle Brachial Index (ABI).

The Ankle Brachial Index(ABI) is the ratio of the blood pressure in the lower legs to the blood pressure in the arms. The ABI is calculated by dividing the systolic blood pressure at the ankle by the systolic blood pressures in the arm.

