6.4 WITHDRAWAL / DISCONTINUATION CRITERIA

Participants have the right to withdraw from the study treatment at any time for any reason. The Investigator has the right and obligation to withdraw participants from the study treatment in the event of:

1. Adverse event(s) which would, in the judgment of the investigator, require discontinuation of study product(s)
2. Request by the participant or their legally authorized representative (consent withdrawal)
3. Non compliance to the study protocol
4. Participants needs additional medication that would interfere with the study
5. Participant is lost to follow-up

6. The sponsor, or the principal investigator or the Data and Safety Monitoring Board or a government agency such as Health Canada cancels the study.

When a participant withdraws consent after starting the protocol treatment the investigator or delegate should make every effort to contact the participant to determine, as completely as possible, the reason for the withdrawal and to schedule an end-of-study visit for assessing potential adverse events. The participant will be asked to return unused study products and will be switched to standard of care, as per their own treating physician.

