8.2 SAMPLE SIZE CALCULATION

Based on recent data published by Conte et al² we expect that during 1 year of follow up, 54% of participants will experience the primary outcome. A total sample of 40 participants was selected and is within the recommended approach for pilot studies evaluating effects when no prior information upon which to base the sample size is available. This sample size will allow us to detect an absolute 20% reduction in the main clinical outcome with a single sided alpha of 0.2 and power of 0.6 as recommended for pilots studies⁵⁹⁻⁶¹. The study will be considered successful if we can demonstrate a reduction in events in the intervention group supported by changes in biomarkers levels (biological plausibility).

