9.4 DATA MANAGEMENT

Data will be recorded on a paper case report form (CRF) by the research personnel according to the protocol. CRFs will be verified for completeness and accuracy by a research team member not involved in the data collection. Any changes to the CRF will be tracked. Upon completion of data collection and verification of the CRF by the Investigator or designee, data will be entered in an data analysis software. Data will be cleaned and coded prior to analysis by a statistician. Missing data will be queried. Data still missing after queries will be coded appropriately by the statistician. Reports will be prepared prior to Data Safety Monitoring Board (DSMB) meetings including: enrollment per treatment arm, descriptive statistics for demographic data (and other relevant characteristic) to assess that randomization was effective, and a tabulated summary of AEs and SAEs per treatment arm.

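### Section 5.7 lets the investigator of an open-label trial remove non-adherent participants from the study, against 12-month follow-up of all in 6.1, and 8.3 names no as-randomised analysis

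*Combined protocol and SAP*

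**What the plan says.** Four places bear on what happens to a participant who does not take the study drug.

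- Section 5.7: "Non-adherent participants may be removed from the study at the discretion of the primary investigator". It gives no threshold for non-adherence.
- Section 6.1: "All participants will be followed for 12 months following their angioplasty". Section 5.8 agrees on the length of the study, recording medication "from the screening time point until study end at 12 months".
- Section 6.4: "The Investigator has the right and obligation to withdraw participants from the study treatment in the event of" a list of reasons, of which non-compliance with the protocol is the third. The same list contains consent withdrawal and loss to follow-up, so it does not cleanly separate stopping drug from leaving the study.
- Section 5.6: "Drug accountability (pill count & review of diary cards) will be done on Day 90 when the medication is returned". Compliance is also reviewed at Days 7 and 30 (6.2.2, 6.2.3, Appendix 1).

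The primary outcome is a composite of reintervention, above-ankle amputation and restenosis at one year (8.1.1). Overall survival and MACE are secondary, with MACE counted to the final visit (8.1.2). Duplex and ABI are obtained "at 30 days, 6 and 12 months as part of the routine care" (6.3.3).

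On analysis, 8.3 names tests only: a t-test or rank test for continuous outcomes and Fisher's exact test for proportions. It defines no analysis population. Section 8.1.1.3 reports restenosis as time to event, but 8.3 has no method for that. On missing data, 9.4 says: "Data still missing after queries will be coded appropriately by the statistician".

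**The concern.** Study drug lasts 90 days and the primary outcome is read at one year. A participant who stops taking the drug is still informative about the assigned strategy, provided follow-up continues. Section 5.7 gives an investigator who can know the arm a discretionary power, exercised after randomisation, to take that participant out of the study. If it is used as written, study collection of the primary outcome, survival and MACE can stop early, for reasons that may differ between rivaroxaban and clopidogrel. Blinded adjudication (9.5.4) cannot judge outcomes that were never collected.

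Nothing later in the plan makes this good. No text says that removed participants remain in their randomised arm for analysis, and how they count is left to an unstated coding decision. The arms are small, so a few such decisions can rival the effect the trial was sized for. The pilot's outcomes are meant to inform whether a full trial is warranted (sections 3, 9.3 and 11).

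**Working it through.** **Inputs.** From 8.2: 40 participants, 54% expected to have the primary outcome within a year, a 20-point absolute reduction, one-sided alpha 0.20, power 0.6. From 8.3: Fisher's exact test. Assumed: 20 per arm, because no allocation ratio is stated. The documents give no removal rate and no event risk for non-adherers, so both are varied.

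**The plan's own figure.** For 54% against 34% with 20 per arm, the pooled normal approximation gives

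- pooled SE = √(2 × 0.44 × 0.56 / 20) = 0.157
- unpooled SE = √((0.54 × 0.46 + 0.34 × 0.66) / 20) = 0.154
- power = Φ((0.20 − 0.842 × 0.157) / 0.154) ≈ 0.67

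Exact enumeration of the one-sided Fisher test gives 0.569. The stated 0.6 lies between the two. This is not evidence of a material error, and the point here does not depend on it.

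**Follow-up at risk.** Days of study observation lost if removal follows a compliance review:

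- Day 7: 365 − 7 = 358 days, with the three scheduled imaging collections (day 30, months 6 and 12) still to come
- Day 30: 365 − 30 = 335 days, with two collections to come
- Day 90: 365 − 90 = 275 days, with the same two to come

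These are limits on study collection. The examinations may still be done in routine care.

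**Uncertainty in an arm's event proportion.** For k participants removed with no earlier event and no one-year assessment, the width is k/20: 5, 10, 15 or 20 points for k = 1, 2, 3 or 4. Four in one arm equal the planned 20-point difference.

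**Illustration under no true effect.** Both arms have 54% risk. Remove k participants of risk r from one arm; the risk among those retained is p = (20 × 0.54 − k × r) / (20 − k). For k = 3 and r = 0.54, p = 9.18/17 = 0.54. Sum the binomial probabilities of all tables that the one-sided Fisher test rejects at 0.20 in favour of rivaroxaban. Events before removal are ignored. With none removed, rejection is 0.133.

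| Removed, at 54% risk | Dropped | Coded no event | Coded event |
|---|---|---|---|
| 3 from rivaroxaban | 0.116 | 0.268 | 0.053 |
| 3 from clopidogrel | 0.125 | 0.045 | 0.242 |
| 1 from rivaroxaban | 0.108 | 0.171 | 0.101 |
| 1 from clopidogrel | 0.122 | 0.097 | 0.164 |

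With three removed from rivaroxaban, the handling choice alone changes the rejection rate about fivefold (0.268/0.053 ≈ 5). If three are dropped and their risk is not average, the result depends on arm and risk: from rivaroxaban, 0.088 at r = 0.40 and 0.248 at r = 1.00; from clopidogrel, 0.160 and 0.048. Dropping three from each arm at equal risk gives 0.113 to 0.115, so no inflation.

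**The case against.** The best defence is that 5.7 is loose wording. It sits in the study-medication chapter, says only that removal may happen, and could mean removal from study drug, with 6.1 governing follow-up. That reading is possible. But 5.4 uses the narrower term, withdrawal from study treatment, when it means that; 5.8 places study end at 12 months; and nothing says 6.1 overrides 5.7. The text needs settling either way.

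Several stronger readings are tempting, and the documents do not support them.

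- A reader might infer that the plan excludes non-adherers from the analysis. It does not: 8.3 orders no exclusion. It simply does not name the population.
- A reader might take 6.4 as a clean opposite rule. Its list mixes treatment withdrawal with consent withdrawal and loss to follow-up, so it is not.
- A reader might say removal loses the imaging. Sections 6.2.5, 6.2.6 and 6.3.3 describe it as standard or routine care, so it may still take place. What is missing is any statement that the results would be used.
- A reader might infer a bias towards rivaroxaban. At average risk, dropping participants lowers rejection slightly (0.116 or 0.125 against 0.133). Inflation needs unequal removal combined with unusual risk or one-sided coding, and no passage proposes such coding.
- A reader might treat the rejection rates as chances of a false success. Section 8.2 says "The study will be considered successful if we can demonstrate a reduction in events in the intervention group", but the sentence goes on to require support from biomarker changes and sets no significance threshold. The figures are not chances of trial success.

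The time-to-event wording in 8.1.1.3 is a partial answer, since it would use partial follow-up. It covers one component only and has no method or censoring rule behind it.

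**Conclusion.** The conflict between 5.7 and 6.1 is plain on the page, and 6.4 does not resolve it. The plan should be changed, because a discretionary removal power in an open-label trial can cut off one-year outcomes selectively by arm, with no as-randomised analysis stated to contain the damage.

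Confidence is high on the text and limited on the consequence. The removal rate and the direction of bias are unknown. The 5 points per participant assume 20 per arm and hold only where no event came before removal, since an earlier reintervention, amputation or restenosis already settles the composite. The illustration assumes 54% risk in both arms and takes the one-sided 0.20 level from 8.2, because 8.3 states neither level nor sidedness. Counting events seen before removal would shrink the effects. With one removal at average risk, rejection stays between 0.097 and 0.171; with three from one arm, the choice of handling matters a good deal.

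**What to change.** Reconcile 5.7 with 6.1 and 6.4. No rule for stopping study drug is proposed here. The reconciled text should say that non-adherence or stopping study drug does not end outcome follow-up: this continues to month 12, using routine-care imaging and records, unless the participant withdraws consent to follow-up.

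In 8.3, make the primary analysis all randomised participants in their assigned arm, counting events observed before any loss to follow-up. Any on-treatment analysis should be a sensitivity analysis only. Report the number lost by arm and two bounds for the primary outcome: all missing counted as events, and all counted as no event. That would give the coding decision left open in 9.4 a visible range.

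The cost is a few wording changes and a few extra follow-up contacts, which the protocol already allows by phone at day 30, month 6 and month 12. Phone contact cannot supply ABI or duplex, so some restenosis data may still be missing and the bounds would still be needed.

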5.8 CONCOMITANT MEDICATIONS

Medication that the participant is taking from the screening time point until study end at 12 months will be recorded by the Research Coordinator. This includes any herbal supplements and vitamins and over the counter medications.

6 STUDY PROCEDURES AND EVALUATIONS

6.1 STUDY VISITS

All participants will be followed for 12 months following their angioplasty. Participants will return to The Ottawa Hospital or will be evaluated as an inpatient at 7 days. There are follow up visits at 30 days, 90 days, 6 months, and 12 months post randomization. All primary and secondary outcome data will be collected during the trial (7 days, 30 days, 90 days, 6 months and 12 months) so that procedures can be evaluated and optimized for future studies. The schedule of study events is summarized in a table in appendix 1.

6.2 SCREENING (-30 DAYS TO -1 DAY OF PTA)

Participants will be screened within 30 days of the PTA procedure.

The following will occur at the screening visit:

- Physical examination (Height and Weight plus BMI)
- Demographics (age, gender, race)
- Tobacco use
- Medical History including:
 - Bleeding history
 - History of stroke, TIA, CAD, CKD, COPD, Hypercholesterolemia
 - History of acute coronary syndrome
- Medication history
- Previous tissue loss
- Co-morbidities including
 - Exclusion criteria
 - Hypertension
 - Obesity
 - Diabetes
- Disease severity (Rutherford scale) and ABI index from medical record

- Anatomic level of disease⁵⁶.
- Obtain bloodwork results for CBC, coagulation tests (INR, PTT), and serum creatinine

6.2.1 Study Day 1: PTA, Randomization/Treatment Day 1

All participants enrolled in the study will receive a loading dose of 325 mg of ASA and IV heparin as per TOH protocol prior to the procedure.

Once the surgeon has completed the PTA +/- stent, participants will be randomized using a web-based program as per section 5.2. Participants will receive study medication as per section 5.3.1 and 5.3.2 for the group to which they are allocated.

At randomization the research coordinator will provide the appropriate training for each participant on:

- Monitoring of outcome events and adverse events.
- Review signs and symptoms of bleeding and provide instructions and study contact numbers.
- Details of the study requirements (follow-up schedule) and the importance of follow-up
- Storage and administration of study drug
- How to complete the Medication Diary

Data collected at Day 1 :

- Vascular access specifications: Access routes, size of introducer sheaths used, specifications of device used (length and diameters of balloons/devices implanted)
- Device to artery ratio for balloons and implants, length of treated segment
- Immediate procedural outcome
- Bleeding (approximate blood loss)
- Concomitant medications
- Blood collection (stored for future evaluation of platelet activation , coagulation markers. smooth muscle activation markers and inflammation markers)

6.2.2 Study Day 7 (+/-3 days)

Data collected :

- Adverse Events
- Drug compliance review
- Blood collection (stored for future evaluation of platelet activation , coagulation markers. smooth muscle activation markers and inflammation markers)

6.2.3 Study Day 30 (+/- 14 days) (may be conducted by phone)

Data collected :

- Disease severity (Rutherford scale)
- Major Cardiac events
- TVR
- TLR
- Amputation
- Bleeding

- Adverse Events
- Compliance
- Concomitant medications
- Ultrasound + ABI index

6.2.4 Study Day 90 (- 14 days)

Data collected :

- Major Cardiac events
- TVR
- TLR
- Amputation
- Bleeding
- AEs
- Compliance
- Concomitant medications
- Blood collection (stored for future evaluation of platelet activation , coagulation markers. smooth muscle activation markers and inflammation markers)

Study treatment will be discontinued and subsequent treatment will be at the discretion of the attending physician (long term use of ASA, as an example).

6.2.5 Study Month 6 (+/-30 days) (may be conducted by phone)

Data collected :

- Disease severity (Rutherford scale)
- Major Cardiac events
- TVR
- TLR
- Amputation
- Bleeding
- Ultrasound + ABI index (standard of care)

6.2.6 Study Month 12(+/-30 days): Final Visit (may be conducted by phone)

Data collected :

- Disease severity (Rutherford scale)
- Major Cardiac events
- TVR
- TLR
- Amputation
- Bleeding
- Ultrasound + ABI index (standard of care)

6.2.7 Premature Discontinuation Visit

In case of premature discontinuation participants will be asked to come for a final visit to assess potential adverse events and return unused study medication.

6.3 OUTCOME MEASURES

6.3.1 Rutherford scale

Participants will be evaluated according to Rutherford scale at screening, and at the day 30, month 6 and month 12 follow-up visits.

Classes in the Rutherford scale are defined as:

- Stage 0 – Asymptomatic
- Stage 1 – Mild claudication
- Stage 2 – Moderate claudication – The distance that delineates mild, moderate and severe claudication is not specified in the Rutherford classification, but is mentioned in the Fontaine classification as 200 meters.
- Stage 3 – Severe claudication
- Stage 4 – Rest pain
- Stage 5 – Ischemic ulceration not exceeding ulcer of the digits of the foot
- Stage 6 – Severe ischemic ulcers or frank gangrene

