4 STUDY DESIGN

This is an open label single center randomized controlled pilot study.

4.1 INCLUSION CRITERIA:

1. Written informed consent and able to comply with protocol.
2. Infra-inguinal PAD presenting as CLI defined with Rutherford category of ≥ 1 .
3. More than 50% stenosis in the target infrainguinal vessel
4. Participant must be a good candidate for PTA using POBA (plain old balloon angioplasty) with or without stenting defined as TASC a, b, c and d lesions.

4.2 EXCLUSION CRITERIA:

1. Acute limb-threatening ischemia (e.g. embolic disease)
2. Hybrid procedures
3. Creatinine clearance <30 mL/min
4. Platelet count $<100 \times 10^9/L$; Hbg < 100 g/L.

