8.1.2 Secondary Outcomes

1. Clinical improvement defined as cumulative improvement of 2 classes of the Rutherford scale without the need for repeated TLR in surviving patients.
2. Event-free survival
3. Overall survival
4. Target lesion revascularization (TLR) between day 1 and final visit
5. Target vessel revascularization (TVR) between day 1 and final visit
6. Peri-procedure death within 30 days
7. Cumulative rate of major adverse cardiovascular events (as defined in 8.1.2.1) between day 1 and final visit
8. Cumulative rate of major bleeding (as defined in 8.1.2.2) between day 1 and day 90.
9. Cumulative rate of minor bleeding (as defined in 8.1.2.2) between day 1 and day 90
10. Biological plausibility by measuring coagulation changes and SMC proliferation markers within 7 and 90 days based on the following markers: D-dimer, soluble CD40/44 ligands, and ERK 1/2.
11. Patency rates based on the ABI index and with an ultrasound at 6 and 12 months
12. Information about feasibility of a future study:
 - a. The total number of eligible candidates identified;

- b. The percentage of eligible patients referred to our study;
- c. The percentage of eligible patients who consent to be enrolled

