9.5.4 Adjudication of outcomes

The primary outcome, bleeding events and major adverse cardiovascular events will be adjudicated by a blinded expert adjudication committee.

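### Rutherford stages 1 to 3 have no working boundary, no blinded rater is specified, and the class is outside blinded adjudication, so the first secondary outcome is open to rater bias at follow-up

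*Combined protocol and SAP*

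**What the plan says.** Section 6.3.1 lists stages 1, 2 and 3 as mild, moderate and severe claudication and then states: "The distance that delineates mild, moderate and severe claudication is not specified in the Rutherford classification". The sentence continues "but is mentioned in the Fontaine classification as 200 meters", without making that distance a rule for this trial.

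Item 1 of section 8.1.2 is "Clinical improvement defined as cumulative improvement of 2 classes of the Rutherford scale without the need for repeated TLR in surviving patients".

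On blinding, section 4 states: "This is an open label single center randomized controlled pilot study". Section 9.4 says "Data will be recorded on a paper case report form (CRF) by the research personnel according to the protocol", with no mention of masking. No section says who assigns the Rutherford class.

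Section 9.5.4 does provide blinded judgement for other outcomes: "The primary outcome, bleeding events and major adverse cardiovascular events will be adjudicated by a blinded expert adjudication committee". The Rutherford class is not on that list.

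Section 6.3.1 schedules the class at screening, day 30, month 6 and month 12. Appendix 1 adds Day 1. The day 30, month 6 and month 12 visits may all be held by phone.

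**The concern.** A grade with no written boundary depends on the judgement of whoever assigns it. If that person may know the arm, the placement can drift in favour of one arm with no true difference between treatments. The plan already accepts that outcomes in this open-label trial need blinded judgement, and it has a committee for the purpose, but this judgement-based outcome is not sent to it.

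At stake is a clinical-improvement result that could look like benefit. Section 9.3 has the Steering Committee review the trial's outcomes when it decides whether a full trial is justified, so a biased result could enter that decision.

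**Working it through.** The plan gives no figure to reproduce for this outcome. The check has two parts: which participants the undefined boundaries reach, and how much a drift in grading could matter.

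**1. Reach of the undefined boundaries**

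Reading a two-class improvement against the baseline class b, success requires a follow-up class of b − 2 or lower. The undefined cuts lie between stages 1 and 2 and between stages 2 and 3.

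| Baseline | Needs | Boundary that decides success | Undefined? |
|---|---|---|---|
| 1 | not possible | none | – |
| 2 | 0 | 0/1 | no |
| 3 | 1 or lower | 1/2 | yes |
| 4 | 2 or lower | 2/3 | yes |
| 5 | 3 or lower | 3/4 | no |
| 6 | 4 or lower | 4/5 | no |

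The follow-up threshold rests directly on an undefined cut for baseline stages 3 and 4 only. Sorting claudicants into stages 1 to 3 at baseline is also undefined. However, screening comes before the procedure (section 6.2) and randomization after it (section 5.2), so knowledge of the arm cannot bias the screening grade. Arm-driven bias enters at follow-up.

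The entry criterion in section 4.1 admits Rutherford category 1 or higher, so baseline stages 3 and 4 are both eligible. The documents give no expected mix of baseline stages, so the share of participants affected cannot be computed.

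**2. Which part of the outcome is unprotected**

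Item 1 combines the class change with freedom from repeat target lesion revascularization (TLR). Section 8.1.1.1 classifies reinterventions as TLR among other types, and reintervention is a component of the primary outcome, which section 9.5.4 sends to the blinded committee. The TLR condition therefore overlaps with an adjudicated event. The element left without blinded judgement is the class itself.

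**3. Illustration of size (assumed inputs)**

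Assumptions: 40 participants split 20 and 20; true improvement of 50% in both arms; 20% to 30% of one arm sitting one class short; 20% to 50% of those graded one class better.

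Apparent rate = true rate + (share one class short × share up-graded)
- Low: 0.50 + 0.20 × 0.20 = 0.54
- High: 0.50 + 0.30 × 0.50 = 0.65

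Section 8.3 names Fisher's exact test for proportions. The rejection rate is the sum, over all pairs (x, y) with p-value at or below alpha, of Bin(x; 20, apparent rate) × Bin(y; 20, 0.50).

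| Apparent rate vs 50% | One-sided, 0.2 | Two-sided, 0.05 |
|---|---|---|
| 50% (no bias) | 0.134 | 0.020 |
| 54% | 0.197 | 0.025 |
| 60% | 0.318 | 0.049 |
| 65% | 0.439 | 0.092 |

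Section 8.2 gives the one-sided 0.2 for the main clinical outcome only. The protocol sets no alpha for secondary outcomes, so both columns use an assumed threshold.

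**The case against.** The strongest case on the other side is that this is one of 12 secondary items in a 40-participant pilot. The success criterion in section 8.2 is a reduction in events supported by biomarker changes, and Rutherford improvement is not part of it. That stands, and it limits the severity.

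Three stronger readings are tempting but go beyond the documents.

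- A reader might infer that the class is graded by unblinded staff. The documents never name the rater. The open-label design, the coordinator's role in training participants on their study drug (section 6.2.1) and the compliance review at the same day 30 visit make it likely. What the text supports is only that no blinded rater is specified.
- A reader might infer that every two-class improvement turns on the undefined cuts, including a move from stage 5 to stage 3. That move turns on the boundary between rest pain and claudication, which section 6.3.1 separates by symptom.
- A reader might take the rejection rates as established inflation of the type I error. They rest on assumed drift and an assumed alpha. At the low end, 0.197 does not exceed 0.2; what is lost there is the conservatism of the exact test. At two-sided 0.05, the rate passes nominal only towards the top of the range.

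It is also fair to say that committee grading would not remove all bias. Participants know their arm and may report by phone. This weakens the remedy but does not answer the gap.

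**Conclusion.** The point holds in a limited form. Stages 1 to 3 have no operative boundary, no blinded rater is specified, and the class is not covered by blinded adjudication. Secondary outcome 1 is therefore open to rater bias at follow-up, directly for participants at baseline stage 3 or 4 and only through the class, not the TLR condition.

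On the assumptions shown, apparent improvement of 54% to 65% against a true 50% moves the one-sided rejection rate at 0.2 from 0.13 to between 0.20 and 0.44, and the two-sided rate at 0.05 from 0.020 to between 0.025 and 0.092. These figures show what could happen; they do not estimate the bias in this trial.

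The effect on the full-trial decision is indirect, through the Steering Committee's review of outcomes (section 9.3). Severity is minor to moderate.

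**What to change.** - **Section 6.3.1:** at each grading, record the reported walking distance, rest pain and tissue loss, not only a stage. Fix one pair of distance cut-offs for stages 1 to 3 before any grading starts. Tying the timing to unblinding would have no clear meaning in an open-label trial.
- **Section 9.5.4:** add the Rutherford class to the list, assigned by the existing blinded committee from these records with the arm removed.
- **Section 8.1.2, item 1:** state that the committee's class is the one analysed.
- **Baseline:** state whether the screening or the Day 1 grade is the baseline, since section 6.3.1 and Appendix 1 differ. Randomization also falls on Day 1, and Appendix 1 does not say whether that grade comes before it.

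**Cost:** 40 participants × 4 time points = 160 short gradings, or 40 × 5 = 200 if Day 1 is kept, plus a few CRF lines. No new assessor, visit or test is needed.

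**Downside:** bias remains from participants who know their arm, from phone visits, and from notes written by staff who may know the arm. The report should state this as a limitation.
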